As stated above, due to the potential affects that COVID-19 has on patients, ie increased risk of clotting, COVID-19 status will be recorded if available via medical record review also at follow up. Research team member will record whether the patient is experiencing any symptoms related to COVID-19 or has tested positive. This data will be collected on all patients who have enrolled into the study since January 2020.

Lost to follow up participants

A percentage of participants will fall in the category where they cannot be contacted, do not return to clinic, or return to clinic but do not have 90 days of follow-up. Additional contact methods will be used to verify these participants' death status which is critical for determining the primary outcome, all-cause mortality. The following methods, which are also described in more detail below, will be used to assess outcomes on these individuals: (1) medical record review, (2) postcard questionnaire, (3) phone call or text follow up from coordinator (4) search via LexisNexis Accurint system, (5) phone call and text message follow up from MCC, (6) search via Limited Access Death Master File (LADMF)

Medical Record Review

If the participant cannot be contacted and does not return for a final research visit, medical records will be abstracted through the last orthopaedic encounter occurring between anytime from the last clinical encounter to the time of medical record review. The visit occurring closest to the 3 month follow-up target should be recorded(e.g. for a participant seen at 60 days, 185 days and 400 days, the 60 day visit should be recorded to demonstrate use of services in the follow-up interval, and the 185 day visit should be recorded to demonstrate that the participant was alive and free of any orthopaedic events at 185 days and therefore also alive and event-free at 90 days, the date of interest. No other visit data should be recorded. Attempts will be made to obtain medical records or autopsy reports for all participants who are discovered to be deceased at the time of the follow up visit. If the participant died at home, family members will be asked to provide a cause of death, if known. No attempts will be made to follow up with family, and the deaths will be recorded as "unknown" cause.

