The MCC will obtain identifiers such as but not limited to the patient's name, date of birth, social security number, and last known address using a secure, encrypted, password-protected File Transfer Protocol. The identifier will be used to conduct probabilistic mapping through public and proprietary database search. Any identifiers will aid in specialized mapping of this database will be used in the search, and the database will return up to date mailing and phone contact information for the participant, as well as any publicly reported deaths.

Phone call/text message follow up (Centralized through MCC)

The MCC will centrally contact each participant and emergency contact, when necessary to evaluate the death status of the participant using the contact phone numbers previously provided by participating centers for weekly follow up as well as information obtained from the Accurint search. Clinical sites may also obtain any additional phone numbers associated with the participant's medical record and transfer it, along with the study ID number, to the MCC using a secure, encrypted, password-protected File Transfer Protocol. All statues will be saved in REDCap. Sample of the text message/call script is in Attachment I.

Search via Limited Access Death Master File (LADMF)

The PREVENT CLOT study protocol is the confidential intellectual property of the PREVENT CLOT Principal Investigators, Steering Committee, and the University of Maryland Baltimore and METRC and cannot be used in any form without the expressed permission of the Principal Investigators.

There will be a subset of patients who cannot be contacted AND have no evidence of any further encounters with the clinical system. For these cases, ascertaining final death status is critical to the validity of the study, and the study team has developed a plan to allow sites to obtain this information while conforming to local policies regarding the sharing of PHI and accessing available data. Because this study is being executed in 21 trauma centers, including 2 centers in Canada, the method for determining if a patient passed away during the study interval will vary. Local IRBs will review the protocol and make a determination regarding if and how this information will be obtained, according to the following options:

- A. Sites have the option to send a secure, encrypted password-protected LOOK-UP File to the MCC for a centralized database search of the Limited Access Death Master File (LADMF).

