3. the number of patients not enrolled and associated reasons
4. the number of enrolled and randomized patients
5. number randomized to aspirin group, number randomized to low-molecular-weight heparin (LMWH) group
6. within treatment group, the number of late ineligibles, late refusals, and inappropriate enrollments
7. within treatment group, the number initiating treatment protocol
8. within treatment group, information on 90 day follow-up (including separate metrics for key endpoints)
9. within treatment group, the number included in the per-protocol analysis

The independent adjudication committee will make the final determination on late ineligibles and inappropriate enrollments while masked to the treatment arm. Late ineligibles and inappropriate enrollments will be removed from all analyses. The outcomes, complications, adverse events of late ineligibles and inappropriate enrollments who received treatment will be reported, to the extent possible.

3 Follow-up Time

Patients were expected to return for a study follow-up visit at 90 days post admission. If participants are unable to return to the clinic, they may be contacted to complete the 90 days follow up visit via phone or email. In addition, medical record reviews will be conducted to determine whether there was documented clinical/research contact beyond the last study follow-up visit. If that visit occurred less than 90 days following randomization, the end of follow up will be defined as the last study follow-up visit or the last clinical/research contact if applicable, and follow-up time will be the duration between randomization and the end of follow up. A figure showing the distribution of follow-up time through 90 days by treatment group will be produced. Differences between treatment groups based on follow-up time through 90 days will be evaluated. Details of reasons for premature study discontinuation will be presented.

4 Baseline Characteristics

A table will report summary statistics of baseline characteristics of participants by treatment groups. Characteristics will include age, sex, body mass index, tobacco use, history of venous thromboembolism, co-morbidities, additional medications, health insurance status, injury severity score, and injury region.

5 Adherence to Treatment Protocol

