7.1 Ascertainment

The primary way in which clinical outcome events are ascertained is through standard of care clinical interactions, medical record review, review of the Limited Access Death Master File records, other available death registries, and, in some cases, phone calls.

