7.3 Estimands

Throughout this section, death is considered as an event that preempts the observation of any future events. In contrast, we consider those individuals lost-to-followup as being at-risk for future events.

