7.3.1 Intention to Treat Analysis

Our primary analysis will use an intention to treat approach. The primary estimand (1) will be estimated using treatment-specific Kaplan-Meier estimators. The other intention-to-treat estimands will be estimated using

treatment-specific cumulative incidence function estimators. The study has more than 90% power to address Estimand (1).

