7.3.2 Primary Estimand

All-Cause Mortality

1. Difference (aspirin minus LMWH) in the probability of dying due to any cause by 90 days for eligible patients under assigned treatment, in a world without loss-to-followup.

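### Used as the Kaplan-Meier censoring rule, SAP 3 would count deaths found by search but censor search-negative patients early, against protocol 6.3.1; Option A also links no date of death

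*Combined protocol and SAP*

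**What the plan says.** **SAP.** Section 3 defines follow-up time. When the follow-up visit falls before day 90, "the end of follow up will be defined as the last study follow-up visit or the last clinical/research contact if applicable". Visits, phone or email contact and record review are mentioned; death-record searches are not. Section 7.1 lists as sources of outcome events "review of the Limited Access Death Master File records, other available death registries, and, in some cases, phone calls". Section 7.3 says "we consider those individuals lost-to-followup as being at-risk for future events". Section 7.3.1 adds: "The primary estimand (1) will be estimated using treatment-specific Kaplan-Meier estimators". The quantity estimated is the difference "in the probability of dying due to any cause by 90 days for eligible patients under assigned treatment", in a hypothetical setting with no loss (7.3.2). Section 2 expects 90-day follow-up to be reported separately by endpoint, but does not define it for death.

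**Protocol v11.0, 6.3.1.** For lost patients, record review, postcards, calls and a commercial database search are followed by a death-file search under Option A (central), B (local) or C (none). The search is presented as the way to establish the primary outcome. Only Option C leaves that outcome missing. For a later medical visit the inference is written out: a patient seen at day 185 is "alive and free of any orthopaedic events at 185 days and therefore also alive and event-free at 90 days". No matching sentence covers a search that finds no death. Under Option A, only the study identifier and the death status go back to the study database. The text introducing the options says "the method for determining if a patient passed away during the study interval will vary".

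**The concern.** A Kaplan-Meier analysis needs an event time or a censoring time for every patient. Take two lost patients, both last seen on day 14 and both searched. One is found to have died on day 60. Under SAP 7.1 that death is an event, and the patient stays in the risk set until day 60. The other search finds nothing. If SAP 3 is the censoring rule, that patient leaves the risk set on day 14. Whether follow-up stops early then depends on the outcome, which the estimator does not allow for. The risk set after last contact is too small for the deaths counted in it, so mortality is overstated.

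The date is a second gap. A status with no date cannot place a death before or after day 90, or give it a time on the curve. Both points bear on the primary endpoint, which is tested against a 0.75-point margin with a stated error below 2.5%.

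**Working it through.** **1. The passages side by side**

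| Place | What it implies for a completed search with no death found |
|---|---|
| SAP 3 | Follow-up ends at last contact; no exception for a search |
| SAP 7.1 | Silent on negative searches; deaths found are events |
| SAP 7.3 | Lost patients remain at risk; no censoring date |
| Protocol 6.3.1, Options A and B | Search settles the primary outcome |
| Protocol 6.3.1, Option C | The only option called missing |
| Protocol 10.3 | No missing death data expected, which needs a negative search to count as known |

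The protocol passages agree with each other. SAP 3 is the one that differs, if it is applied to death.

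**2. The plan's own figures**

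Inputs: 6,100 per arm (protocol 5.1), 1.0% baseline mortality (10.1), margin 0.75% and a two-sided 96.2% interval (SAP 7.4; z = 2.075).

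- Equal risk: SE = sqrt(2 x 0.01 x 0.99 / 6,100) = 0.180 points. Then 0.75/0.180 - 2.075 = 2.09, so power is 98.2%. The protocol says more than 95% and SAP 7.3.1 more than 90%.
- True risks 1.75% v 1.00%: the error is 1.9% by formula and 2.0-2.1% by simulation. The protocol says less than 2.5%.

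Both figures reproduce.

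**3. Size of the overstatement if SAP 3 is the censoring rule**

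Let p be the true 90-day risk, f the share of deaths after last contact, and L the share of patients whose status rests on a search alone. Assume the search finds every death. After last contact:

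- deaths = f p
- at risk = (1 - L)[1 - (1 - f)p] + L f p
- Kaplan-Meier risk = 1 - [1 - (1 - f)p] x [1 - deaths / at risk], roughly p[1 + f L/(1 - L)]

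Assumptions not in the documents: last contact at day 14, and f from 0.70 to 0.84 (constant hazard gives 76/90 = 0.84). L is also not given. The only stated attrition is 7.5% in total, for the original calculation, so L = 7.5% is an upper guess.

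- L = 7.5%, f = 0.84: at risk = 0.925 x 0.9984 + 0.075 x 0.0084 = 0.9242; 0.0084/0.9242 = 0.00909; risk = 1 - 0.9984 x 0.99091 = **1.07%**. With f = 0.70 it is 1.06%.
- L = 2.5%, f = 0.84: 1.00% x (1 + 0.84 x 0.025/0.975) = **1.02%**.
- L = 7.5% with last contact at day 42 or 60 (constant hazard): 1.04% or 1.03%.

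In patients, L = 7.5% means 6,100 x 0.075 x 0.01 x f = 3 to 4 search-found deaths by day 90 in the LMWH arm, and 6 to 7 on aspirin at 1.75%.

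**4. Effect on the decision**

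With equal loss, a true difference of zero stays at zero. A true 0.75 points reads as about 0.75 x 1.068 = 0.80, which makes non-inferiority harder to claim. Simulated error at the margin (at least 200,000 trials per scenario, Greenwood variance, single final look, equal 7.5% loss):

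| Scenario | SAP 3 as censoring rule | Search-negative followed to day 90 | All search-only patients censored, later registry deaths dropped |
|---|---|---|---|
| All deaths found | 1.2-1.3% | 2.0-2.1% | 2.0-2.2% |
| Half of late deaths missed | 1.5-1.6% | 2.5-2.7% | 2.0-2.1% |
| Lost patients at twice the late risk, all found | 1.2-1.3% | 2.0-2.1% | 3.0-3.3% |

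At 2.5% equal loss with all deaths found, the SAP 3 reading gives about 1.7%. Power at equal risk and 7.5% loss is 96.5-96.8%, against 98.1% for the day-90 rule.

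**5. Undated Option A deaths**

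If every linked death counted whatever its date, each arm would rise by (share resolved by Option A alone) x (share dying after day 90 but before the search). With assumed ranges of 1-2.5% and 1-5%, that is 0.01 x 0.01 = 0.01 points up to 0.025 x 0.05 = 0.13 points. The difference does not move if these shares are equal in both arms.

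**The case against.** The best defence is that SAP 3 was never meant as the censoring rule for death. It supports a figure and a comparison of follow-up between arms, mentions neither Kaplan-Meier nor censoring, and sits beside a CONSORT item that expects follow-up to differ by endpoint. Protocol 6.3.1 makes the intention plain: a completed search means the outcome is known. On the date, the study interval is named as the target, the coordinating center holds the randomization dates, and the sentence limiting what is linked reads as a privacy limit. A flag for death at any time is the least natural reading. Protocol 10.3 also promises sensitivity analyses.

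Most of this stands. It is why the overstatement is conditional on how SAP 3 is used, and why the date point is about what is written rather than what was intended. It does not remove the gap. SAP 3 is the only place that says when follow-up ends for a patient without 90 days of contact, and an analyst programming from the SAP would reach it first. A registry search is not a contact. Nothing says that Option A status is set against day 90 before linking, and even a status set that way gives no Kaplan-Meier time. The analyses in 10.3 do not say which rule is primary.

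**Conclusion.** The point holds as a minor to moderate one. SAP 3, used as the censoring rule alongside SAP 7.1, makes censoring depend on outcome and overstates each arm's mortality: about 1.02% for a true 1.00% at 2.5% search-only loss, and at most 1.07% at 7.5%. It also conflicts with protocol 6.3.1. Option A as written does not link what the analysis needs. The sizes rest on last contact at day 14, the assumed share of later deaths and, for L, a guess bounded by total attrition; later last contact makes them smaller.

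Three stronger readings are not supported.

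- A reader might infer that the non-inferiority test is compromised. At equal loss the SAP 3 reading is conservative (about 1.2-1.7%) and power stays above 95%. With 5% search-only loss on aspirin and 10% on LMWH the error is 2.4%, still inside the stated bound. Reaching up to 4.0% takes 5% against 15%, and nothing in the documents suggests such a split.
- A reader might infer that the plan gives no direction at all. The protocol points clearly to a completed search meaning outcome known; only the SAP sentence is missing.
- A reader might infer that deaths after day 90 will be counted. The stated aim is the study interval. The date point is also confined to Option A: the text on Option B and the commercial database does not say whether dates are kept.

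**What to change.** 1. In protocol 6.3.1, Option A, also link the date of death, or days from randomization to death, and count only deaths by day 90.
2. In SAP 3, for Estimand 1 only, state that a patient with a completed search covering day 90 and no death found is followed to day 90, in line with protocol 6.3.1, and that Option C patients are censored at last contact.
3. As one of the sensitivity analyses already promised in protocol 10.3, censor all search-only patients at last contact and leave out registry-only deaths after it. Report the number of search-only patients by arm.

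The third item should not be the primary rule. It discards known deaths from an all-cause mortality endpoint, contrary to SAP 7.1, and it relies on loss being unrelated to death.

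The cost is one extra field in the look-up return, a sentence or two in the SAP before unblinding, and one extra run. The downside to state openly is that the day-90 rule understates mortality when searches miss deaths. With 7.5% loss and half of late deaths missed, 1.00% reads as 1.00% x (1 - 0.075 x 0.84 x 0.5) = 0.97%, and the error at the margin rises to about 2.7%, slightly above the stated 2.5%. The sensitivity analysis holds 2.0-2.1% in that case, which is why both should be shown. The two do not strictly bracket the truth.

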7.1 Ascertainment

The primary way in which clinical outcome events are ascertained is through standard of care clinical interactions, medical record review, review of the Limited Access Death Master File records, other available death registries, and, in some cases, phone calls.

7.2 Adjudication

For our secondary outcome of cause-specific death, all deaths will be adjudicated into one of the following five categories in terms of certainty of a pulmonary embolism (PE): (a) Certainly PE, (b) More likely PE than something else, (c) Equally likely to be PE than something else, (d) More likely something else than PE and (e) Definitely not PE. For patients in categories (d) or (e), adjudicators will indicate the most likely cause of death.

7.3 Estimands

Throughout this section, death is considered as an event that preempts the observation of any future events. In contrast, we consider those individuals lost-to-followup as being at-risk for future events.

7.3.1 Intention to Treat Analysis

Our primary analysis will use an intention to treat approach. The primary estimand (1) will be estimated using treatment-specific Kaplan-Meier estimators. The other intention-to-treat estimands will be estimated using

treatment-specific cumulative incidence function estimators. The study has more than 90% power to address Estimand (1).

7.3.2 Primary Estimand

All-Cause Mortality

1. Difference (aspirin minus LMWH) in the probability of dying due to any cause by 90 days for eligible patients under assigned treatment, in a world without loss-to-followup.

7.3.3 Secondary Efficacy Estimands

Cause-Specific Mortality

2. Difference (aspirin minus LMWH) in the probability of being *observed* to die due to PE (using categories a and b from Section 7.2) by 90 days for eligible patients under assigned treatment, in a world without loss-to-followup;
3. Difference (aspirin minus LMWH) in the probability of being *observed* to die due to PE (using categories a, b and c from Section 7.2) by 90 days for eligible patients under assigned treatment, in a world without loss-to-followup;
4. Difference (aspirin minus LMWH) in the probability of being *observed* to die due to non-PE (must be in category d or e from Section 7.2) causes of death (e.g., myocardial infarction, stroke, bleeding) by 90 days for eligible patients under assigned treatment, in a world without loss-to-followup;

Non-Fatal Pulmonary Embolism

5. Difference (aspirin minus LMWH) in the probability of being *observed* to have a non-fatal PE by 90 days for eligible patients under assigned treatment, in a world without loss-to-followup, where non-fatal PE will be categorized in (i) aggregated, (ii) sub-classified as massive, sub-massive, clinically significant, clinically non-significant and (iii) sub-classified as segmental, non-segmental;

Deep Vein Thrombosis

6. Difference (aspirin minus LMWH) in the probability of being *observed* to have a DVT by 90 days for eligible patients under assigned treatment, in a world without loss-to-followup; where DVT will be categorized as (i) any, (ii) proximal, and (iii) distal.

7.3.4 Secondary Safety Estimands

Major Bleeding Event

7. Difference (aspirin minus LMWH) in the probability of being *observed* to have a bleeding event by 90 days for eligible patients under assigned treatment, in a world without loss-to-followup;

Wound Complication

8. Difference (aspirin minus LMWH) in the probability of being *observed* to have a wound complication by 90 days for eligible patients under assigned treatment, in a world without loss-to-followup.

Deep Surgical Site Infection

9. Difference (aspirin minus LMWH) in the probability of being *observed* to have a deep surgical site infection by 90 days for eligible patients under assigned treatment, in a world without loss-to-followup;

7.3.5 Per Protocol Analysis

To understand treatment differences in the presence of non-adherence, we will perform a secondary per protocol analysis for the nine estimands. The per protocol estimands will only include the subset of patients classified as protocol adherent, as defined in Section 5. To the extent possible, we will adjust for a limited set of key baseline covariates. Missing baseline covariates will be imputed using multiple imputation.

7.4 Analytic Strategy

- We will test Estimand 1 for non-inferiority using the upper bound of a two-sided 96.2% confidence interval compared to the pre-specified non-inferiority margin of 0.75%.
- If non-inferiority is established at our pre-specified non-inferiority margin, we will test for superiority.
- Two-sided 95% confidence intervals will also be presented for Estimands 2-9 but null-hypothesis significance tests will not be performed.

7.5 Subgroup Analyses

We will perform one subgroup analysis to assess the variation in treatment effect for our primary outcome based on patient age:

1. Age > 60 vs. Age ≤ 60

Interaction tests will be performed to assess heterogeneity of treatment effects.

7.6 Comments

- Due to low event rates, it may be impossible to compute reliable confidence intervals.
- We recognize that precision can be increased by leveraging baseline covariates. To the extent possible, we will leverage age, injury severity, and other key characteristics.

8 Change in Primary Outcome

The primary study outcome was changed from PE-related death to all-cause mortality during the course of the trial.

At the recommendation of an external peer reviewer for the protocol manuscript, the trial's steering committee determined that it was infeasible to adjudicate death due to pulmonary embolism (PE) with reasonable certainty. Misclassification of the primary outcome of PE-related death would bias the results to non-inferiority. As such, the trial's steering committee decided to change the primary outcome from PE-related death to all-cause mortality. All-cause mortality was viewed as more important than PE-related death by our patient stakeholder and protocol committees and had greater scientific reliability. The change in the primary outcome increased the anticipated base rate from 0.25% to 1.00% leading to an increase in the non-inferiority margin from 0.36% to 0.75% to maintain the target sample size of 12,200 and over 90% power. The DSMB was not involved in these decisions due to their masked knowledge of treatment effect from interim analyses. The decision of the trial's steering committee to change the primary outcome and non-inferiority margin was supported by the protocol committee, patient stakeholder committee, and sponsor.

Prepared by:

[name] (ScD), Principal Biostatistician

Approved by:

[name] (MD), Principal Investigator

[name] (PhD), Co-Principal Investigator.

[name] (MD, MPH), Co-Principal Investigator

[name] (MHA), Co-Investigator
